Protocol Title: A Phase 2, Multiple Cohort Study of Elotuzumab in Combination with Pomalidomide and Low-Dose Dexamethasone (EPd), and in Combination with Nivolumab (EN), in Patients with Multiple Myeloma Relapsed or Refractory to Prior Treatment with Lenalidomide.

Investigational Product(s), Dose and Mode of Administration, Duration of Treatment with Investigational Product(s):

Elotuzumab: 10 mg/kg IV - Cycles 1 and 2: Days 1, 8, 15, 22

20 mg/kg IV - Cycle 3 and beyond: Day 1 of each cycle

Pomalidomide: 4 mg PO: Days 1 - 21 of each cycle

Dexamethasone: Days 1, 8, 15, and 22 of each cycle:

- Subjects \leq 75 years old: Weeks with elotuzumab dosing: 28 mg PO + 8 mg IV and 40 mg PO on non-elotuzumab dosing weeks
- Subjects > 75 years old: Weeks with elotuzumab dosing: 8 mg PO + 8 mg IV and 20 mg PO on non-elotuzumab dosing weeks

Nivolumab:

- Cycles 1 through 4: 240 mg IV Days 1, 15 of each 28-day cycle
- Cycles 5 and beyond: 480 mg IV Day 1 of each 28-day cycle

Study Phase: Phase 2

Research Hypothesis:

Elotuzumab/Pomalidomide/Low-Dose Dexamethasone Cohort (EPd) :

Elotuzumab in combination with pomalidomide and low-dose dexamethasone will prolong progression-free survival (PFS) in subjects with multiple myeloma (MM) who have relapsed or are refractory or intolerant to a lenalidomide-based regimen.

Elotuzumab/Nivolumab Cohort (EN):

The combination of elotuzumab and nivolumab will provide clinical benefit, represented by response rate, in patients with relapsed or refractory multiple myeloma (MM) who have received at least 4 prior lines of therapy including a proteasome inhibitor (PI), immunomodulatory (IMID), and an anti-CD38 antibody.

Objectives:

Primary EPd Cohort Objective:

• To estimate the PFS in patients with MM treated by EPd as second- or third-line regimen after relapse or being refractory or intolerant to a prior lenalidomide based regimen.

Primary EN Cohort Objective:

• To estimate the Objective Response Rate (ORR).

Secondary EPd Objectives

- Estimate the ORR
- Estimate the overall survival (OS) Rate

Secondary EN Cohort Objectives:

- Estimate PFS
- Estimate OS

Study Design:

This is a Phase 2, multi-center, open-label, multiple cohort study of elotuzumab in combination with pomalidomide and low dose dexamethasone (EPd Cohort) and elotuzumab in combination with nivolumab (EN Cohort) to assess the safety and efficacy of this combination therapy for treatment of relapsed or refractory MM patients.

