4.5.4 Nivolumab

Nivolumab will be administered at a dose of 240 mg as an intravenous infusion over 30 minutes every 2 weeks (Days 1 and 15 of each 28 day cycle) during Cycles 1 through 4. Starting Cycle 5 and beyond, nivolumab will be administered at a dose of 480 mg as an intravenous infusion over 30 minutes every 4 weeks (Day 1 of each 28 day cycle).

Nivolumab should be administered before elotuzumab.

When administering Q2W, subjects may be dosed no less than 12 days from the previous dose. There are no premedications recommended for nivolumab on the first cycle.

Nivolumab can be delayed within a 3 day window of Day 1 and Day 15, during cycles 1 through 4, as long as the 12 day interval between 2 nivolumab doses is respected.

When administering Q4W, subjects may be dosed no less than 21 days from the previous dose. During cycles 5 and beyond, nivolumab can be delayed within a week.

Doses that fall outside the allowed window, regardless of the schedule, should be skipped.

Subjects should be carefully monitored for infusion reactions during nivolumab administration. If an acute infusion reaction is noted, subjects should be managed according to Section 4.5.6.

There will be no dose escalations or reductions of nivolumab allowed. Doses of nivolumab may be interrupted, delayed, or discontinued in accordance with Section 4.5.8 depending on how well the subject tolerates the treatment.

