4.5.8.4 Dose Delay for Nivolumab

Nivolumab administration should be delayed for the following:

- Any Grade ≥ 2 non-skin, drug-related adverse event, with the following exceptions:
 - Grade 2 drug-related fatigue or laboratory abnormalities do not require a treatment delay/ interruption.
- Any Grade 3 skin, drug-related adverse event
- Any Grade 3 drug-related laboratory abnormality, with the following exceptions for lymphopenia, AST, ALT, or total bilirubin or asymptomatic amylase or lipase:
 - Grade 3 lymphopenia does not require dose delay/interruption
 - If a subject has a baseline AST, ALT, or total bilirubin that is within normal limits, delay/interrupt dosing for drug-related Grade ≥ 2 toxicity.
 - If a subject has baseline AST, ALT, or total bilirubin within the Grade 1 toxicity range, delay/interrupt dosing for drug-related Grade \geq 3 toxicity.
 - Any Grade \geq 3 drug-related amylase or lipase abnormality that is not associated with symptoms or clinical manifestations of pancreatitis does not require dose delay/interruption.
- Any adverse event, laboratory abnormality, or intercurrent illness which, in the judgment of the investigator, warrants delaying the dose of study medication.

Revised Protocol No.: 03 Date: 08-Mar-2018 Subjects who require delay/interruption of nivolumab should be re-evaluated as clinically indicated and resume nivolumab dosing, as per the protocol dosing schedule when re-treatment criteria are met.

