4.5.8.6 Nivolumab Dose Discontinuation

Nivolumab treatment should be permanently discontinued for the following:

- Any Grade 2 drug-related uveitis, eye pain or blurred vision that does not respond to topical therapy and does not improve to Grade 1 severity within the re-treatment period OR requires systemic treatment
- Any Grade 3 non-skin, drug-related adverse event lasting > 7 days, with the following exceptions for laboratory abnormalities, drug-related uveitis, pneumonitis, bronchospasm, hypersensitivity reactions, infusion reactions, and endocrinopathies:
 - Grade 3 drug-related uveitis, pneumonitis, bronchospasm, hypersensitivity reaction, or infusion reaction of any duration requires discontinuation
 - Grade 3 drug-related endocrinopathies adequately controlled with only physiologic hormone replacement do not require discontinuation
 - Grade 3 drug-related laboratory abnormalities do not require treatment discontinuation except:
 - Grade 3 drug-related thrombocytopenia > 7 days or associated with bleeding requires

discontinuation

- Any drug-related liver function test (LFT) abnormality that meets the following criteria require discontinuation:
 - AST or ALT > 5-10 x ULN for 2 weeks
 - AST or $ALT > 10 \times ULN$
 - Total bilirubin > 5 x ULN
 - Concurrent AST or $ALT > 3 \times ULN$ and total bilirubin $> 2 \times ULN$
 - Any Grade 4 drug-related adverse event or laboratory abnormality, except for the following events which do not require discontinuation:
- Grade 4 neutropenia \leq 7 days
- Grade 4 lymphopenia or leukopenia
- Isolated Grade 4 amylase or lipase abnormalities that are not associated with symptoms or clinical manifestations of pancreatitis. The BMS Medical Monitor should be consulted for Grade 4 amylase or lipase abnormalities.
- Isolated Grade 4 electrolyte imbalances/abnormalities that are not associated with clinical sequelae and are corrected with supplementation/appropriate management within 72 hours of their onset
- Grade 4 drug-related endocrinopathy adverse events, such as adrenal insufficiency, ACTH deficiency, hyper- or hypothyroidism, or glucose intolerance, which resolve or are adequately controlled with physiologic hormone replacement (corticosteroids, thyroid hormones) or glucose-controlling agents, respectively, may not require discontinuation after discussion with and approval from the BMS Medical Monitor.

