CBC, differential, platelets	Х	X	Х	X		Can be drawn up to 3 days prior to study visit (See Section 5.3.4). Screening results are sufficient for Cycle 1
Chemistry	Х					Can be drawn up to 3 days prior to study visit
Pregnancy Test	Х					For WOCBP only. Urine tests must have a sensitivity of at least 25 IU/L. Test within 24 hours of Dose 1 study medication.

Table 5.1-4:CA204142 Cycles 1 and 2 - EN Cohort

Procedure	Day 1	Day 8	Day 15	Day 22	Rest Days 23 – 28	Notes					
Thyroid stimulating hormone (TSH) (reflex to free T3/total T3, free T4 for abnormal TSH result).	X*					To be performed every *2 cycles (± 7 days) from first dose regardless of dosing schedule					
Efficacy Assessments											
Myeloma Urine and		(C	entral La	b Analy	sis)	Day 1 of each cycle (Optional at C1D1 if conducted at screening.)					
Serum Lab tests	~ . I	Ever	y 4 week	s from d	ate of .	(See also: Section 5.4.2)					
Igs)	first dose of study drug until disease progression of study drug until disease progression regardless of whether subject is on study therapy or subsequent therapy					24-hour urine sample can be collected within \pm 7 days of visit, and must be obtained in all subjects					
Bone Marrow	For confirmation of CR, if applicable or, if					Bone Marrow plasma cell percentage.					
Aspiration/Biopsy	clinically indicated at time of suspected disease progression (Local Lab analysis)					Performance of IHC or flow cytometry to assess for sCR (for subjects with CR).					
Corrected Calcium	Every of study of wh	4 weeks drug untinether th s	from the il disease e subject ubsequer	date of progres is on stu t therap	the first dose of sion, regardless udy therapy or y.	Serum calcium and albumin from peripheral blood at D1 of each cycle until disease progression, even if subject is on subsequent therapy; if used as criterion for disease progression, must be confirmed by second value.					
Skeletal Imaging		If	clinically	y indicat	ted						
CT/MRI assessment	As clini	cally inc	licated ar assess	nd at the ments	time of CR/sCR						

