5.3 Safety Assessments

Only data for the procedures and assessments specified in this protocol should be submitted to BMS. Additional procedures and assessments may be performed as part of standard of care; however, the data for these assessments should remain in the subject's medical record and should not be provided to BMS, unless specifically requested from the Sponsor. Safety assessments must be done prior to dosing. The local safety labs (complete blood count, chemistry panel) and procedures may be collected or performed up to 3 days prior to the visit. For subjects who skip a dose, local safety labs results must be submitted to BMS at least once per cycle. In addition, all safety lab results that lead to dose delay or discontinuation must be submitted to BMS.

All subjects will be assessed for safety. Safety evaluations include assessments of AEs, clinical laboratory tests (hematology, chemistry), vital sign measurements, and physical examination with assessment of ECOG PS. Investigators are responsible for monitoring the safety of subjects who have entered this study and for alerting the Sponsor to any event that seems unusual, even if this event may be considered an unanticipated benefit to the subject. The investigator is responsible for appropriate medical care of subjects during the study.

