5.3.4 Laboratory Assessments for Safety

Laboratory assessments for safety will be performed at local laboratories. Safety laboratory assessments are listed in Table 5.3.4-1.

Safety Laboratory Assessments		
	Screening as outlined in Table 5.1-1. Within 14 days of first dose of study drug	Study Visits as outlined in Table 5.1-2,Table 5.1-3, Table 5.1-4, Table 5.1-5, and Table 5.1-6.
Hematology		
CBC	Х	Х
Differential	Х	Х
Platelets	Х	Х
Chemistry		
Sodium	Х	Х
Potassium	Х	Х
Chloride	Х	Х
Albumin	Х	Х
	(within 28 days of first dose of study drug)	
Alkaline Phosphatase	Х	Х
ALT (SGPT)	Х	Х
AST (SGOT)	Х	Х
Total Bilirubin	Х	Х
Lactate Dehydrogenase	Х	Х
BUN (or Urea)	Х	Х
Creatinine	Х	Х
Glucose	Х	Х
Calcium	Х	Х
Pregnancy Test		
Urine or Serum Pregnancy	X (2 tests: one 10 - 14 days prior to the start of study drug and one within 24 hours prior to the start of study drug)	X Pregnancy test must also be performed at end of treatment, and at 30, 60 and 90 days off treatment. The test at 90 days off treatment may be performed locally if the patient is not scheduled to return to the center for other reasons. Urine tests must have a sensitivity of at least 25 IU/L.
Hepatitis B surface antigen (HBV sAg, Australia antigen) and hepatitis C antibody (HCV Ab) or HCV ribonucleic acid (RNA)	X ^a	

Table 5.3.4-1:Safety Laboratory Assessments

Revised Protocol No.: 03 Date: 08-Mar-2018

Safety Laboratory Assessments		
	Screening as outlined in Table 5.1-1. Within 14 days of first dose of study drug	Study Visits as outlined in Table 5.1-2,Table 5.1-3, Table 5.1-4, Table 5.1-5, and Table 5.1-6.
Thyroid stimulating hormone (TSH) (reflex to free T3, free T4 or abnormal result)	X ^a	X ^b

Table 5.3.4-1: Safety Laboratory Assessments

^a Within 28 days of first dose of study drug

^b TSH (reflex to free/total T3, free T4 for abnormal result) to be performed every 2 cycles (\pm 7 days) from first dose regardless of schedule.

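### EN cohort: nivolumab is given on Days 1 and 15 of Cycles 1 to 4 but chemistry is scheduled on Day 1 only, so the schedule does not supply the laboratory values that the protocol's own nivolumab rules use at Day 15

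*Protocol*

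**What the plan says.** **Dosing.** The Protocol synopsis gives nivolumab as "Cycles 1 through 4: 240 mg IV Days 1, 15 of each 28-day cycle". Section 4.5.4 agrees: "every 2 weeks (Days 1 and 15 of each 28 day cycle) during Cycles 1 through 4". Table 4.5-2 shows the same days. From Cycle 5, nivolumab moves to Day 1 only.

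**Laboratory schedule.** In Table 5.1-4 (EN, Cycles 1 and 2) chemistry has one mark, under Day 1, with the note "Can be drawn up to 3 days prior to study visit". The CBC row directly above is marked on Days 1, 8, 15 and 22, and its note adds "Screening results are sufficient for Cycle 1". In Table 5.1-5 (EN, Cycles 3 and 4) both chemistry and CBC are marked on Day 1 only, while vital signs, adverse events, serious adverse events and concomitant medications are also marked on Day 15.

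**Laboratory list.** Section 5.3.4 says "Safety laboratory assessments are listed in Table 5.3.4-1". For on-study timing that table refers back to the Section 5.1 tables, so it adds no draw.

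**Rules that use the results.** Section 5.3 says "Safety assessments must be done prior to dosing". Section 4.5.8.4 contains the delay rule "If a subject has a baseline AST, ALT, or total bilirubin that is within normal limits, delay/interrupt dosing" for drug-related toxicity of Grade 2 or worse, and a general delay rule for Grade 3 drug-related laboratory abnormalities, with exceptions. Section 4.5.8.6 says "Any drug-related liver function test (LFT) abnormality that meets the following criteria require discontinuation", lists limits for AST, ALT and total bilirubin as multiples of the upper limit of normal, and adds rules for Grade 3 thrombocytopenia and for Grade 4 laboratory abnormalities.

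**The concern.** The delay and discontinuation rules turn on laboratory grades, and every nivolumab dose is a point at which they could apply. At Day 15 of Cycles 1 to 4 the schedule supplies no chemistry taken after the preceding nivolumab dose. In Cycles 3 and 4 it supplies no blood count either, although elotuzumab is then given on Day 1 only, so the Day 15 infusion visit exists for nivolumab alone.

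Section 1.5 names hepatotoxicity and nephrotoxicity among the nivolumab risks and ties their manageability partly to frequent monitoring. A rise in liver enzymes without symptoms may not emerge from the adverse event questioning that is scheduled on Day 15. A site that keeps exactly to the tables can therefore give the dose without knowing whether a delay or discontinuation criterion is met.

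**Working it through.** The plan states no figure on this point, so the check is a count of scheduled doses against scheduled draws.

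**Inputs**
- Nivolumab days per cycle, Cycles 1 to 4: 2 (synopsis, Section 4.5.4, Table 4.5-2).
- Chemistry days per cycle: 1, Day 1 (Tables 5.1-4 and 5.1-5).
- CBC days per cycle: 4 in Cycles 1 and 2 (Days 1, 8, 15, 22); 1 in Cycles 3 and 4 (Day 1).
- Draw window: up to 3 days before the visit.
- Nivolumab may be delayed within a 3-day window of Day 15 (Section 4.5.4).
- Planned EN subjects: about 30 (Section 8.1.2).

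**Doses and draws**
- Nivolumab doses in Cycles 1 to 4: 4 × 2 = 8.
- Doses with chemistry scheduled at the visit: 4 × 1 = 4.
- Doses with no chemistry scheduled since the previous dose: 8 − 4 = 4, so 4/8 = 50%.
- Doses with no CBC scheduled since the previous dose: Day 15 of Cycles 3 and 4, so 2/8 = 25%.

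**Age of the latest scheduled chemistry at a Day 15 dose**
- Drawn on Day 1: 15 − 1 = 14 days.
- Drawn 3 days before Day 1: 14 + 3 = 17 days.
- If the Day 15 dose also slips by its 3 days: 17 + 3 = 20 days.

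In each case the sample precedes the Day 1 nivolumab dose.

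**Number of doses in the cohort**
- Ceiling: 30 × 4 = 120 Day 15 doses, if every subject completes Cycle 4 with no dose skipped.
- If every subject instead crossed over after Cycle 2, as Section 3.3.4 permits without a minimal response: 30 × 2 = 60. Skipped doses or earlier withdrawal would lower either figure.

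**Could the blank cell come from the way the table was read?** This is unlikely. In Table 5.1-4 the adjacent CBC row keeps its Day 15 mark, and in Table 5.1-5 four safety rows keep theirs. The draw-window note does not itself show the gap; the single Day 1 mark in the same row does.

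**From Cycle 5** dosing and chemistry both fall on Day 1 (Table 5.1-6), so the mismatch is confined to Cycles 1 to 4.

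**The case against.** **Section 5.3 may already cover it.** After asking for safety assessments before dosing, Section 5.3 names the blood count and chemistry panel as local safety laboratory tests. It also requires results at least once per cycle from subjects who skip a dose, which suggests that testing otherwise follows dosing. On that reading a site would test before Day 15. On the narrower reading, Section 5.3 only orders the scheduled assessments relative to the dose, and the tables do not breach it. Both readings are tenable. This stands to the extent that a flat contradiction with Section 5.3 cannot be claimed. It does not remove the gap, because neither reading puts a Day 15 chemistry mark in the tables and the two lead to different practice.

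**Investigators have other safeguards.** Adverse events are assessed before dosing on Day 15, an investigator may delay for any abnormality or illness, and extra tests are allowed as standard of care. This stands against any claim that affected patients will be dosed. The supportable wording is that they can be, and that doses lack scheduled chemistry rather than chemistry altogether.

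**Readings that go too far**
- *Renal rules.* A reader might infer that the nivolumab rules contain a renal limit that goes unchecked. Sections 4.5.8.4 to 4.5.8.6 name none. Creatinine enters only through the general Grade 3 and Grade 4 laboratory rules. Section 4.5.7 points to a renal algorithm in Appendix 7, which is not in the text available here.
- *Two-week criterion.* A reader might set the 28-day chemistry interval against the two-week duration condition for AST and ALT in Section 4.5.8.6. Once an abnormality leads to a delay, Section 4.5.8.4 leaves re-evaluation to clinical need, outside the routine schedule. The gap concerns first detection.
- *Cohort stopping rule.* A reader might infer that late detection would defeat Section 4.5.10. That rule uses a cumulative proportion in the first half of treated patients, with events assessed to 100 days after nivolumab. The documents give no event rate, and nothing shows that a delay of about two weeks would change whether or when the rule is met.

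**Conclusion.** The point holds as an internal mismatch that should be resolved. Four of the 8 nivolumab doses in Cycles 1 to 4 have no chemistry scheduled since the previous dose, and 2 of those 4 also have no blood count scheduled. The latest scheduled chemistry is about 14 days old, or about 17 with an early draw. The case is strongest for AST, ALT and total bilirubin, for which explicit limits are written. For other chemistry and blood counts it rests mainly on the general graded rules.

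The conclusion assumes that the table marks are complete as read and that no instruction in unavailable text, Appendix 7 in particular, schedules Day 15 tests. The figure of 120 doses is a ceiling, not an expected count. How many patients would be dosed while meeting a criterion cannot be estimated from the documents.

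**What to change.** Reconcile the chemistry and CBC rows of Tables 5.1-4 and 5.1-5 with Sections 5.3, 4.5.8.4 and 4.5.8.6, so that the schedule states which laboratory results must be available before each nivolumab dose. Section 5.3 should be worded so that sites cannot read it two ways. The content of that requirement is for the sponsor to decide; no dose, delay or discontinuation criterion is proposed or changed here.

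The cost is an amendment to two rows in each of two tables, plus a clarifying sentence. If the sponsor chooses to align the tables to the rules, the added burden would be at most four local chemistry panels and two blood counts per EN subject (one panel per cycle over Cycles 1 to 4, one count per cycle over Cycles 3 and 4). These would fall at visits already attended for an infusion, and blood is already drawn on Day 15 in Cycles 1 and 2.

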5.1.1 Retesting During Screening Period

Retesting of laboratory parameters and/or other assessments within any single Screening period will be permitted (in addition to any parameters that require a confirmatory value).

Any new result will override the previous result (ie, the most current result prior to Treatment) and is the value by which study inclusion will be assessed, as it represents the subject's most current, clinical state.

Laboratory parameters and/or assessments that are included in Screening Procedural Outline may be repeated in an effort to find all possible well-qualified subjects. Consultation with the Medical Monitor may be needed to identify whether repeat testing of any particular parameter is clinically relevant.

5.2 Study Materials

The following will be distributed to sites for use in this study:

- Instructions and kits for collections, processing, and shipment of blood and tissue samples
- NCI CTCAE booklets version 3.0
- Elotuzumab Investigator Brochure
- Nivolumab Investigator Brochure
- Pomalidomide (Pomalyst®) Package Insert
- Site Manual for operation of IVRS
- Subject Dosing Diary
- Serious Adverse Event (SAE) Case Report Form (CRF/eCRF) pages
- Pregnancy Surveillance Forms

5.3 Safety Assessments

Only data for the procedures and assessments specified in this protocol should be submitted to BMS. Additional procedures and assessments may be performed as part of standard of care; however, the data for these assessments should remain in the subject's medical record and should not be provided to BMS, unless specifically requested from the Sponsor. Safety assessments must be done prior to dosing. The local safety labs (complete blood count, chemistry panel) and procedures may be collected or performed up to 3 days prior to the visit. For subjects who skip a dose, local safety labs results must be submitted to BMS at least once per cycle. In addition, all safety lab results that lead to dose delay or discontinuation must be submitted to BMS.

All subjects will be assessed for safety. Safety evaluations include assessments of AEs, clinical laboratory tests (hematology, chemistry), vital sign measurements, and physical examination with assessment of ECOG PS. Investigators are responsible for monitoring the safety of subjects who have entered this study and for alerting the Sponsor to any event that seems unusual, even if this event may be considered an unanticipated benefit to the subject. The investigator is responsible for appropriate medical care of subjects during the study.

